10.2 Response and Evaluation Endpoints

Response and progression will be evaluated in this study using the revised international criteria (1.1) proposed by the RECIST (Response Evaluation Criteria in Solid Tumours) committee.

10.2.1 Measurable Disease. Measurable *tumour lesions* are defined as those that can be accurately measured in at least one dimension (longest diameter to be recorded) as ≥ 20 mm with chest x-ray and as ≥ 10 mm with CT scan or clinical examination. Bone lesions are considered measurable only if assessed by CT scan and have an identifiable soft tissue component that meets these requirements (soft tissue component ≥ 10 mm by CT scan). *Malignant lymph nodes* must be ≥ 15 mm in the short axis to be considered measurable; only the short axis will be measured and followed. All tumour measurements must be recorded in millimetres (or decimal fractions of centimetres). Previously irradiated lesions are not considered measurable unless progression has been documented in the lesion.

10.2.2 Non-measurable Disease. All other lesions (or sites of disease), including small lesions are considered non-measurable disease. Bone lesions without a measurable soft tissue component, leptomeningeal disease, ascites, pleural/pericardial effusions, lymphangitis cutis/pulmonis, inflammatory breast disease, lymphangitic involvement of lung or skin and abdominal masses followed by clinical examination are all non-measurable. Lesions in previously irradiated areas are non-measurable, unless progression has been demonstrated.

10.2.3 Target Lesions. When more than one measurable tumour lesion is present at baseline all lesions up to *a maximum of 5 lesions total* (and a maximum of *2 lesions per organ*) representative of all involved organs should be identified as target lesions and will be recorded and measured at baseline. Target lesions should be selected on the basis of their size (lesions with the longest diameter), be representative of all involved organs, but in addition should be those that lend themselves to *reproducible repeated measurements*. Note that pathological nodes must meet the criterion of a short axis of ≥ 15 mm by CT scan and only the *short axis* of these nodes will contribute to the baseline sum. All other pathological nodes (those with short axis ≥ 10 mm but < 15 mm) should be considered non-target lesions. Nodes that have a short axis < 10 mm are considered non-pathological and should not be recorded or followed (see 10.2.4). At baseline, the sum of the target lesions (longest diameter of tumour lesions plus short axis of lymph nodes: overall maximum of 5) is to be recorded. **Note: For this study, skin lesions will be considered as non-target lesions.**

AMEND #1: 2016-NOV-23

After baseline, a value should be provided on the CRF for all identified target lesions for each assessment, even if very small. If extremely small and faint lesions can not be accurately measured but are deemed to be present, a default value of 5 mm may be used. If lesions are too small to measure and indeed are believed to be absent, a default value of 0 mm may be used.

10.2.4 *Non-target Lesions*. All non-measurable lesions (or sites of disease) plus any measurable lesions over and above those listed as target lesions are considered *non-target lesions*. Measurements are not required but these lesions should be noted at baseline and should be followed as “present” or “absent”. **Note: For this study, skin lesions will be considered as non-target lesions.**

10.2.5 *Response*.

All patients will have their BEST RESPONSE from the start of study treatment until the end of treatment classified as outlined below:

Complete Response (CR): disappearance of *target* and *non-target* lesions and normalization of tumour markers. Pathological lymph nodes must have short axis measures < 10 mm (*Note*: continue to record the measurement even if < 10mm and considered CR). Residual lesions (other than nodes < 10 mm) thought to be non-malignant should be further investigated (by cytology specialized imaging or other techniques as appropriate for individual cases *[Eisenhauer 2009]* before CR can be accepted. Confirmation of response is only required in non-randomized studies.

Partial Response (PR): at least a 30% decrease in the sum of measures (longest diameter for tumour lesions and short axis measure for nodes) of target lesions, taking as reference the baseline sum of diameters. Non target lesions must be non-PD. Confirmation of response is only required in non-randomized studies.

Stable Disease (SD): Neither sufficient shrinkage to qualify for PR nor sufficient increase to qualify for PD taking as reference the smallest sum of diameters on study.

Progressive Disease (PD): at least a 20% increase in the sum of diameters of measured lesions taking as references the smallest sum of diameters recorded on study (including baseline) AND an absolute increase of $\geq 5\text{mm}$. Appearance of new lesions will also constitute progressive disease (including lesions in previously unassessed areas). In exceptional circumstances, unequivocal progression of non-target disease may be accepted as evidence of disease progression, where the overall tumour burden has increased sufficiently to merit discontinuation of treatment or where the tumour burden appears to have increased by at least 73% in volume. Modest increases in the size of one or more non-target lesions are NOT considered unequivocal progression. If the evidence of PD is equivocal (target or non-target), treatment may continue until the next assessment, but if confirmed, the earlier date must be used.

Patients that are clinically well may continue on therapy following RECIST progression with new lesions or increase in target lesions if the increase in disease burden does not meet the definition of PD by immune response criteria *[Seymour 2016]*. In this situation, patients do not have unequivocal progression until immune response criteria are met (see Table 2 below).

AMEND #1: 2016-NOV-23

Table 1: Integration of Target, non-Target and New Lesions into Response Assessment:

Target Lesions	Non-Target Lesions	New Lesions	Overall Response	Best Response for this Category also Requires
Target lesions ± non target lesions				
CR	CR	No	CR	Normalization of tumour markers, tumour nodes <10mm
CR	Non-CR/Non-PD	No	PR	
CR	Not all evaluated	No	PR	
PR	Non-PD/ not all evaluated	No	PR	
SD	Non-PD/ not all evaluated	No	SD	documented at least once \geq 4 wks. from baseline
Not all evaluated	Non-PD	No	NE	
PD	Any	Any	PD	
Any	PD	Any	PD	
Any	Any	Yes	PD	
Non target lesions ONLY				
No Target	CR	No	CR	Normalization of tumour markers, tumour nodes < 10mm
No Target	Non-CR/non-PD	No	Non-CR/non-PD	
No Target	Not all evaluated	No	NE	
No Target	Unequivocal PD	Any	PD	
No Target	Any	Yes	PD	
Note: Patients with a global deterioration of health status requiring discontinuation of treatment without objective evidence of disease progression at that time should be reported as "symptomatic deterioration". This is a reason for stopping therapy, but is NOT objective PD. Every effort should be made to document the objective progression even after discontinuation of treatment.				

Immune-Related Response Assessment

Overall response will also be assessed using iRECIST [Seymour 2016]. Immunotherapeutics may result in infiltration of immune cells leading to transient increase in the size in malignant lesions, or undetectable lesions becoming detectable. The criteria are identical to those of RECIST 1.1 in many respects but have been adapted to account for instances where an increase in tumour burden, or the appearance of new lesions, does not reflect true tumour progression.

Key differences are described below. All responses defined using iRECIST criteria are designated with a prefix. iRECIST time-point and best overall responses will be recorded separately.

AMEND #1: 2016-NOV-23

Confirming Progression

Unlike RECIST 1.1, iRECIST requires the confirmation of progression and uses the terms iUPD (unconfirmed progression) and iCPD (confirmed progression). Confirmatory scans should be performed at least 4 weeks, but no longer than 8 weeks after iUPD.

iCPD is confirmed if further increase in tumour burden, compared to the last assessment, is seen as evidenced by one or more of the following:

- Continued increase in tumour burden (from iUPD) where RECIST 1.1 definitions of progression had been met (from nadir) in target, non-target disease or new lesions
 - Progression in target disease worsens with an increase of at least 5 mm in the absolute value of the sum
 - Continued unequivocal progression in non-target disease with an increase in tumour burden
 - Increase in size of previously identified new lesion (s) (an increase of at least 5 mm in the absolute value of the sum of those considered to be target new lesions) or additional new lesions.
- RECIST 1.1 criteria are met in lesions types (target or non-target or new lesions) where progression was not previously identified, including the appearance of additional new lesions.

If iUPD is not confirmed at the next assessment, then the appropriate response will be assigned (iUPD if the criteria are still met, but no worsening, or iSD, iPR or iCR if those criteria are met compared to baseline). As can be seen in table 2, the prior documentation of iUPD does not preclude assigning iCR, iPR, or iSD in subsequent time-point assessments or as best overall response (BOR) providing that iCPD is not documented at the next assessment after iUPD.

New Lesions

New lesions should be assessed and measured as they appear using RECIST 1.1 criteria (maximum of 5 lesions, no more than 2 per site, at least 10 mm in long axis (or 15 mm in short axis for nodal lesions), and recorded as New Lesions-Target (NLT) and New Lesion-Non-Target (NLNT) to allow clear differentiation from baseline target and non-target lesions.

New lesions may either meet the criteria of NLT or NLNT to drive iUPD (or iCPD). However, the measurements of NLT should NOT be included in the sum of measures of original target lesions identified at baseline. Rather, these measurements will be collected on a separate table in the case record form.

PD is confirmed in the New Lesion category if the next imaging assessment, conducted at least 4 weeks (but not more than 8 weeks) after iUPD confirms further progression from iUPD with either an increase of at least 5 mm in the absolute value of the sum of NLT OR an increase (but not necessarily unequivocal increase) in the size of NLNT lesions OR the appearance of additional new lesions.

AMEND #1: 2016-NOV-23

Table 2: Time-point (TP) iResponse

Target Lesions*	Non-Target Lesions*	New Lesions*	Time Point Response	
			No prior iUPD**	Prior iUPD**; ***
iCR	iCR	No	iCR	iCR
iCR	Non-iCR/Non-iUPD	No	iPR	iPR
iPR	Non-iCR/Non-iUPD	No	iPR	iPR
iSD	Non-iCR/Non-iUPD	No	iSD	iSD
iUPD with no change OR decrease from last TP	iUPD with no change OR decrease from last TP	Yes	NA	NLs confirms iCPD if NLs were previously identified and increase in size (≥ 5 mm in SOM for NLT or any increase for NLNT) or number. If no change in NLs (size or number) from last TP, remains iUPD
iSD	iUPD	No	iUPD	Remains iUPD unless iCPD confirmed based in further increase in size of NT disease (need not meet RECIST 1.1 criteria for unequivocal PD)
iUPD	Non-iCR/Non-iUPD	No	iUPD	Remains iUPD unless iCPD confirmed based on: 
 o further increase in SOM of at least 5 mm, otherwise remains iUPD
iUPD	iUPD	No	iUPD	Remains iUPD unless iCPD confirmed based on further increase in: 
 o previously identified T lesion iUPD SOM ≥ 5 mm and / or o NT lesion iUPD (prior assessment - need not be unequivocal PD)
iUPD	iUPD	Yes	iUPD	Remains iUPD unless iCPD confirmed based on further increase in: 
 o previously identified T lesion iUPD ≥ 5 mm and / or o previously identified NT lesion iUPD (need not be unequivocal) and /or o size or number of new lesions previously identified
Non-iUPD/PD	Non-iUPD/PD	Yes	iUPD	Remains iUPD unless iCPD confirmed based on 
 o increase in size or number of new lesions previously identified

* Using RECIST 1.1 principles. If no PSPD occurs, RECIST 1.1 and iRECIST categories for CR, PR and SD would be the same.

** In any lesion category.

*** Previously identified in assessment immediately prior to this TP.

AMEND #1: 2016-NOV-23

Table 3: iRECIST Best Overall Response (iBOR)

All patients will have their iBOR from the start of study treatment until the end of treatment classified as outlined below.

TPR1	TPR2	TPR3	TPR4	TPR5	iBOR
iCR	iCR, iPR, iUPD, NE	iCR, iPR, iUPD, NE	iUPD	iCPD	iCR
iUPD	iPR, iSD, NE	iCR	iCR, iPR, iSD, iUPD, NE	iCR, iPR, iSD, iUPD, iCPD, NE	iCR
iUPD	iPR	iPR, iSD, iUPD, NE	iPR, iSD, iUPD, NE, iCPD	iPR, iSD, iUPD, NE, iCPD	iPR
iUPD	iSD, NE	PR	iPR, iSD, iUPD, NE	iPR, iSD, iUPD, iCPD, NE	iPR
iUPD	iSD	iSD, iUPD, NE	iSD, iUPD, iCPD, NE	iSD, iUPD, ICPD, NE	iSD
iUPD	iCPD	Anything	Anything	Anything	iCPD
iUPD	iUPD	iCPD	Anything	Anything	iCPD
iUPD	NE	NE	NE	NE	iUPD

- Table assumes a randomized study where confirmation of CR or PR is not required.
- NE = not evaluable that cycle.
- Designation “I” for BOR can be used to indicate prior iUPD to aid in data interpretation.
- For patients with non-target disease only at baseline, only CR or non-CR/non-PD can be assigned at each TPR but is not shown in the table for ease of presentation.

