4.0 TRIAL DESIGN

This is an open-label, multicentre, phase II trial of pembrolizumab in first line therapy of metastatic melanoma. This trial is being conducted by the Canadian Cancer Trials Group with the support of Merck.

AMEND #1: 2016-NOV-23

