8.1 Chemotherapy Treatment Plan

8.1.1 Drug Administration

Agent	Route	Starting Dose	Schedule
Pembrolizumab	IV	200 mg	Day 1 every 3 weeks

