9.1 Evaluation During Protocol Treatment

	Investigations	Timing
History and Physical Exam including:	
 history weight ECOG Performance status vital signs (blood pressure and pulse) clinical tumour measurements (if applicable) 	Day 1 each cycle
Hematology*	
 CBC, differential, platelets 	Day 1 each cycle
Biochemistry*	
 electrolytes (sodium, potassium, chloride, bicarbonate) alkaline phosphatase AST, ALT serum creatinine bilirubin 	Day 1 each cycle
	
 phosphorous calcium magnesium albumin 	As clinically indicated
	
 TSH, FT3, FT4 	Every other cycle
Radiology**	
 CT scan with contrast of chest, abdomen/pelvis Other sites as clinically indicated 	4 weeks, 12 weeks, then every 12 weeks
Other Investigations	
 ECG 	As clinically indicated
Economics	
 Health Utilities Index (EQ-5D) Resource Utilization Assessment 	To be completed at each 12 weekly visit until progression OR maximum 1 year from registration
Adverse Events***	Patients must be evaluated after each cycle for adverse events	

* Bloodwork Timing: Pre-treatment blood draws should be done within 72 hours (maximum) prior to treatment.

** Patients with a CR or PR should have scans repeated after minimum 4 weeks to confirm response. See Appendix VII for CT requirements.

*** Adverse events will be recorded and graded according to the NCI Common Terminology Criteria for Adverse Events (CTCAE) (Appendix V).

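### iRECIST best response is classified by a table that assumes a randomised study and waives confirmation of CR and PR, although this trial is non-randomised and its response definitions require confirmation

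*Combined protocol and SAP*

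**What the plan says.** **Design.** Section 4.0 states: "This is an open-label, multicentre, phase II trial of pembrolizumab in first line therapy of metastatic melanoma". Section 8.1.1 lists one agent at one dose, given "Day 1 every 3 weeks". Section 7 describes registration only. No randomisation or second arm appears anywhere.

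**Confirmation of response.** In Section 10.2.5 the CR and the PR definitions each end with the same sentence: "Confirmation of response is only required in non-randomized studies". The footnote to the Section 9.1 schedule reads: "Patients with a CR or PR should have scans repeated after minimum 4 weeks to confirm response". Section 9.2 and Appendix I (footnote 7) repeat that instruction.

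**iRECIST best response.** Table 3 in Section 10.2.5 is introduced with: "All patients will have their iBOR from the start of study treatment until the end of treatment classified as outlined below". The first note beneath it reads: "Table assumes a randomized study where confirmation of CR or PR is not required". No other table or rule for a confirmed iCR or iPR is given.

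**Related text.** A footnote to Table 2 says that, without pseudoprogression, the CR, PR and SD categories under the two criteria would agree. Section 10.3 starts response duration when the criteria for CR/PR or iCR/iPR are first met.

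**The concern.** The note carries a premise that is false for this trial, and the table is introduced as the rule for all patients. The protocol therefore appears to require confirmation for RECIST 1.1 response and to waive it for iRECIST response, for a reason that does not apply here.

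Two things are at stake. First, best response under the two criteria could differ because of unequal confirmation rules and not because of pseudoprogression, which is the reason the protocol gives for using iRECIST. Second, duration of response is a secondary objective, and Section 10.3 lets it start from an iCR or iPR without saying that the response must be confirmed. An analyst would have to choose between following Table 3 as printed and improvising a rule.

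**Working it through.** The plan gives no figure to reproduce here. The check sets the passages side by side and reads Table 3 row by row.

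**Step 1: does the confirmation rule apply to this trial?** The CR and PR definitions make confirmation depend on whether the study is randomised. Sections 4.0, 7 and 8.1.1 describe one regimen given to registered patients. The trial is therefore non-randomised and confirmation is required. The schedule footnotes support this but say only that scans should be repeated, so the firm requirement rests on the definitions in Section 10.2.5.

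**Step 2: what does Table 3 accept?** The fewest responding time points (iCR or iPR) that each response row allows, with one permitted sequence:

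| Row | Permitted sequence | iBOR given | Responding time points |
|---|---|---|---|
| 1 | iCR, NE, NE, iUPD, iCPD | iCR | 1 |
| 2 | iUPD, iSD, iCR, iSD, iSD | iCR | 1 |
| 3 | iUPD, iPR, iSD, iSD, iSD | iPR | 1 |
| 4 | iUPD, iSD, iPR, iSD, iSD | iPR | 1 |

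In row 4 the third time point is printed as PR and is read here as iPR. A confirmed response needs 2 responding scans: the first one and the repeat at least 4 weeks later. All four rows thus apply the note's assumption.

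**Step 3: is the difference consistent with the rest of Section 10.2.5?** Take the row 1 sequence. The progression at the fourth time point is confirmed at the fifth, so there is no pseudoprogression. In RECIST 1.1 terms the patient has a CR that is never repeated, followed by progression, and the CR is unconfirmed. Table 3 nevertheless gives iCR. That conflicts with the principle in the Table 2 footnote that the response categories agree when there is no pseudoprogression. The footnote concerns time-point response, so it supports the principle and does not by itself settle the iBOR rule.

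**Step 4: direction and size.** For any sequence of scans, waiving confirmation can only leave the iRECIST response category unchanged or raise it. The documents give no share of responses that fail confirmation, so the number of patients affected cannot be derived.

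**Step 5: would confirmation need new scans, and does the window allow it?** Section 9.1 schedules CT at "4 weeks, 12 weeks, then every 12 weeks". Within the 1-year treatment maximum of Section 12.2 that means weeks 4, 12, 24, 36 and 48, with intervals of 12 − 4 = 8, 24 − 12 = 12, 36 − 24 = 12 and 48 − 36 = 12 weeks. All exceed the 4-week minimum. A response first seen at week 48, however, cannot be confirmed before week 48 + 4 = 52. That is at or beyond the end of protocol treatment, while iBOR runs only to the end of treatment.

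**The case against.** The strongest defence has three parts.

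**The criteria are meant to differ.** Section 10.1.2 tells investigators that the two criteria have different requirements for confirmatory scans, and does not limit this to progression. The section on immune-related response then says that the key differences follow. Those described concern confirmation of progression and the handling of new lesions. Response confirmation is not among them, so Section 10.1.2 does not justify the waiver. The same silence can be turned around: the Section 10.2.5 rule plausibly carries over to iRECIST, and the note is then only a disclosed simplification. That reading is sensible, and it is the one the fix should make explicit. As printed, though, the note says the opposite and the rows follow it.

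**Table 3 is illustrative.** This stands in part. Seven of its eight rows start with iUPD and one with iCR; none starts with iPR or iSD. A patient with iSD, iPR, iPR has no row. A reader might take the table as a complete classifier of all patients, but it cannot be one, despite the sentence that introduces it. Amending the four response rows alone would therefore not be enough.

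**No named analysis is affected.** This also stands in part. Section 14 specifies no iRECIST response rate and no comparison of the two criteria. The response-rate objective in Section 1.2 names only PR and CR, and iRECIST results are recorded separately. A reader might infer that the reported overall response rate is inflated, or that a planned comparison of the two criteria is biased; the documents support neither. What remains is iBOR itself and duration of response, because Section 10.3 names iCR/iPR.

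**Conclusion.** The inconsistency is real and minor. Table 3 and its note, read literally, hold iRECIST best response to a looser standard than RECIST 1.1 best response, in a trial whose own definitions call for confirmation. Unconfirmed iCR or iPR can also enter duration of response.

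The direction is known and the size is not. RECIST 1.1 best response is untouched by the note.

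A reader might go further and conclude that the responder/non-responder split in the primary texture analysis is distorted. The documents do not show this: neither Section 1.1 nor Section 14 says which criterion defines a responder, so an effect there is possible but not established.

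The conclusion rests on two readings: that the trial is non-randomised, which follows from the single regimen and registration although the protocol does not use that label, and that the introductory sentence makes Table 3 operative for the sequences it shows.

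**What to change.** 1. Remove the note that assumes a randomised study.
2. State that iCR and iPR count as iBOR only when confirmed on the repeat scan at least 4 weeks later, the same rule as for CR and PR in Section 10.2.5.
3. Mark the four iCR/iPR rows of Table 3 accordingly, and say that the rule also applies to sequences not shown, such as those starting with iSD or iPR.
4. State which category an unconfirmed iCR or iPR receives.
5. State whether a confirming scan after the end of treatment counts, since iBOR runs only to the end of treatment and a late response may not be confirmable before then.
6. Make clear in Section 10.3 that iRECIST response duration uses responses that meet this rule.

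If unconfirmed iRECIST response is what the sponsor intends, the text must still change, because the reason given does not fit this design.

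The cost is a change of wording and table. No new response scans are needed, because Sections 9.1, 9.2 and Appendix I already call for the repeat scan. The downside is that the reported iRECIST response rate may be slightly lower.
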